Management of Traumatic Bone Defects in Tibial Plateau Fractures with Antibiotic-Impregnated Biodegradable Calcium Sulfate Beads: A Prospective Clinical Trial

Principal Investigator / Sponsor: [name] M.D.

Other Investigators: Canadian Orthopaedic Trauma Society

Research Coordinators: [name]

[name]

Funder: Biocomposites, Ltd.

Clinical Trial Registration: NCT02456194

Introduction / Background

The tibial plateau is the flattened surface of the top of the tibia bone, which makes it part of the knee joint. It is covered with cartilage, which is critical for the smooth movement of the knee joint. It also houses the menisci ("shock absorbers") of the knee joint and a number of ligaments that act to stabilize the knee joint. Fractures of this bone are difficult to manage since they can disrupt these soft tissues in addition to the bone. Fractures are classified according to their severity. The most common classification of tibial plateau fractures is by Schatzker (Figure 1), with the classification number increasing with severity¹.

[figure not shown]

Figure 1: Schatzker Classification of Tibial Plateau Fractures

Tibial plateau fractures require anatomical reduction of the joint surface and stable fixation to allow early range of motion and progressive weight bearing to facilitate healing². If the tibial plateau fracture involves a depression of the joint surface, elevating the fracture fragment can result in a defect, or void, in the metaphyseal bone. Standard practice is to fill this void with bone graft or a bone graft substitute. Autogenous Iliac Bone Grafting (AIBG) has long been considered the gold standard in subarticular bone defect management in conjunction with conventional open reduction and internal fixation techniques for unstable tibial plateau fractures³

although complications of graft harvest, ranging from temporary pain and numbness to long-term functional impairment, are well documented⁴⁻⁸. These complications, along with the limited availability of AIBG, have led to the development of bone graft substitutes.

Calcium sulfate has been used as a bone substitute for nearly 100 years. It is low cost, readily available, has a structure similar to bone allowing for osteoconductivity, and it has a proven safety record. Calcium sulfate can also be used for local antibiotic delivery for the treatment or prevention of infection⁹.

Advances in trauma care have reduced infection rates in tibial plateau fractures from $80\%^{10}$ to $10 - 14\%^{11}$, but the complex nature of the injury has been shown to be an independent risk factor for infection¹². Preventing colonization of the bone graft used in tibial plateau fractures is desirable. The ability to provide antibiotics locally, rather than systemically, for the duration of the graft remodeling may improve outcomes of this injury if bony healing is not compromised.

We propose a prospective clinical trial of tibial plateau fractures treated with internal fixation and a calcium sulfate graft which can be mixed with antibiotics and molded into various bead sizes for implantation into bone defects. The graft material chosen for this study is STIMULAN Rapid Cure (Biocomposites, UK), which is approved for use as a bone void filler and may be mixed with a variety of antibiotics. The combination of STIMULAN + antibiotic in bead form is herein referred to as the "study device".

Why is a Trial Needed Now?

While studies have been done to look at prevention and treatment of infection with the study device¹³⁻²⁵, there is no published evidence of its effectiveness in acute, closed, non-infected tibial plateau fractures. Previous studies have indicated that calcium sulfate is resorbed by three months after implantation and that bone has remodeled by six months²⁶⁻²⁷. These studies did not include the use of antibiotics in the calcium sulfate.

Study Aims

Our primary study aim is to look at resorption and remodeling of the study device into bone. Another important aim of the study is to look at subsidence, or collapse, of the joint surface. Secondary outcomes are those that are clinically important after this injury including time to bone healing, knee range of motion, knee stability, return to work and activities, infection, wound problems, functional outcomes, and complications.

How Will the Results of This Trial Be Used?

This trial will provide clinical evidence on the use of antibiotics mixed with calcium sulfate in the treatment of acute, closed, non-infected tibial plateau fractures. This will guide orthopaedic surgeons in their clinical decision making for this complex injury.

Methods

This will be a prospective, non-randomized study. Up to four centers in Canada with extensive experience in the treatment of tibial plateau fractures will be selected for this multi-centre study. The study will be an investigator-driven study with QEII Health Sciences Centre as the lead site. It will be supported by an unrestricted research grant from Biocomposites Ltd. with the funds being distributed to all sites via the lead site. Thirty (30) consecutive patients who meet the inclusion criteria will be recruited for the study and followed for one year.

Inclusion Criteria:

Patient selection criteria will include:

- Adult (skeletally mature) men or women;
- Acute, closed, tibial plateau fractures, Schatzker grade 1 through 5;
- Internal fixation and use of study device per protocol;
- Fracture repair within 30 days of injury;
- Signed informed consent to participate in study.

Exclusion Criteria:

- Uncontrolled diabetes;
- Severe degenerative or metabolic bone disease;
- Malignancy;
- Severe vascular or neurologic disease;
- Alcoholism;
- Substance abuse;
- Use of systemic steroids;
- Immunosuppressive therapy;
- Hypercalcaemia;
- Renal-compromised patients;
- Osteomyelitis or chronic infection in the study limb;
- Women who are pregnant or breast-feeding.

All sites will obtain approval from the institutional review board at their respective hospitals and participants will be required to provide informed consent prior to any study procedures. Since the study device is an option for treatment of this injury, informed consent may occur post-operatively if the study device was used per protocol as the standard of care. Patients who consent to participate in study but do not receive the study device will not be considered study participants.

All visits required will be those as per regular follow up visits in their institutions, so no travel expenses should be required. If however extra visits are required for study purposes (e.g. CT scan performed after hours), a small stipend will be paid to cover parking/ travel.

Standard open reduction and internal fixation techniques will be used to restore fracture stability. The implants utilized for this purpose will include locked and unlocked premolded proximal tibial plates and small fragment plates as per the decision of the attending surgeon. Subarticular grafting with the study device will be accomplished via an open procedure. The study device cannot be used alone or with screws only, it must be used with standard internal fixation as noted above.

Preparation of the Study Device

The study device is to be prepared with the antibiotic chosen according to the manufacturer's mixing guidelines (Appendix A). The selection of antibiotic from those in the mixing guidelines is left to the surgeon's discretion. A maximum of one 10cc kit of STIMULAN Rapid Cure per participant is to be used. The STIMULAN is to be prepared in bead form. The selection of bead size is at the discretion of the surgeon.

Post-operative immobilization, weight-bearing, and rehabilitation protocol will be the standard of care for each surgeon.

Follow-up will be scheduled at 6 weeks, 3 months, 6 months, and 12 months as per the usual at each site. Other visits may be "clinically indicated" but would not be required as a part of this study. Baseline information will be collected during the initial hospital stay.

Risks and Benefits of Study Participation

This trial does not involve any experimental devices or procedures. The risks of participating are no greater than standard of care. As with any study, there is a risk of breach of confidentiality. There is no direct benefit to participants in this study. The results of this study will benefit future patients with this injury by providing more evidence on treatment with the study device.

How Will The Outcome Measures Be Measured at Follow-up?

Basic demographic information: At the time of study inclusion, information on basic demographics (age, sex), past medical history, co-morbidities, medications (i.e. bisphosphonates, vitamin D), pre-injury level of activity and/or employment and mechanism of injury will be collected for all participants.

Functional outcomes: The Knee injury Osteoarthritis Outcome Score (KOOS)²⁸ is a validated self-administered questionnaire which will be completed at the designated follow-up visits. The questionnaire completion time is approximately 15 minutes. Return to work and return to preinjury activities will be measured in weeks.

Clinical outcome: Range of motion will be evaluated and will include active and passive flexion and extension. Knee stability will be assessed. The surgical site will be examined for progression in healing, wound issues (drainage, dehiscence, etc.) or signs of infection.

Radiological outcome: Evaluation will be performed at each participating centre and all radiographs will be sent to the principal investigation centre with all identifiers removed. Exams at each study visit will be the standard AP and lateral radiographs. Amount of study device remaining and percent remodeled will be measured on plain radiographs. Time to union will be defined as bridging callus evident on two x-rays. Our previous study on tibial plateau fractures indicated that subsidence occurs between three and six months after surgery²⁹. Therefore, at six months a CT scan will be performed to determine if any study device remains and to measure any subsidence of the joint surface.

Adverse Events: Since the study device is being used according to the indications for use, monitoring of adverse events will be according to standard clinical practice. Reporting of serious adverse events will be according to the REB policy at participating sites, with copies sent to the lead site and the Quality Department at Biocomposites. Adverse events of interest in the study are those associated with the surgical procedure and healing of the injury.

Data Collection, Management, and Retention

Each study participant will be assigned a unique Subject ID to safeguard confidentiality. The Subject ID will be used on all data collection forms. Subject IDs will be assigned consecutively at each site. Participating sites will be provided with a site number and all the required Case Report Forms prior to initiation. Completed CRFs and questionnaires from each study site will be sent via Fax or e-mail to the lead site after each patient follow-up visit, according to the data transfer and/or sub-site agreement in effect. Sites will also be given the option to enter deidentified data directly into REDCap. Study sites will keep the originals and file them in the subject binder at each site. Radiographic images (x-rays and CT) for each subject will be deidentified and copied onto a compact disc (CD) and submitted to the lead site at the end of the study. See Appendix B for schedule of events.

Data management will be coordinated from the lead site (QEII Health Sciences Centre). Study data will be managed using REDCap electronic data capture tools hosted by Nova Scotia Health Authority. REDCap (Research Electronic Data Capture) is a secure, web-based application designed to support data capture for research studies, providing 1) an intuitive interface for validated data entry; 2) audit trails for tracking data manipulation and export procedures; 3) automated export procedures for seamless data downloads to common statistical packages; and 4) procedures for importing data from external sources. Sites will be given a choice to either continue to send CRF's to the lead site or they will be given dedicated login information and training on how to access the REDCap tool and enter data directly into REDCap.

Study documents will be retained for seven (7) years. Sites will store and maintain all study-related documents according to local policies, guidelines, and standards. Destruction of study records will be in accordance with local policies.

Analysis of Results

All analysis will be performed at the lead site. Descriptive statistics will be used to describe the study sample. Patients will be evaluated as to union, subsidence, loss of graft or premature resorption, percent of graft remaining at each visit, knee range of motion, knee stability, loss of fixation or fixation failure, infection, functional recovery (outcome scores and return to work, return to activity) and effect of tobacco use, age, sex, fracture classification. The sample size of thirty participants was chosen based on the expected recruitment rate at this site and others planning to participate in the interest of providing objective evidence of the healing potential with this device in patients with this injury.

References

- 3. Segal, D., A. V. Franchi, et al. (1985). "Iliac autograft for reconstruction of severely depressed fracture of a lateral tibial plateau. Brief note." *J Bone Joint Surg Am* 67(8): 1270-2.
- 4. Younger, E., Chapman, MW (1989). "Morbidity at bone graft donor sites." *J. Orthop Trauma* 3: 192-195.

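### Does making per-protocol device use an entry criterion leave the fate of patients implanted outside the limits, and so the denominator, undefined?

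*Combined protocol and SAP*

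**What the plan says.** The Methods section plans a non-randomized study at up to four centres: "Thirty (30) consecutive patients who meet the inclusion criteria will be recruited". The Inclusion Criteria contain "Internal fixation and use of study device per protocol" and signed consent.

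The limits on use come after the eligibility text. On fixation: "The study device cannot be used alone or with screws only". Under Preparation of the Study Device: "A maximum of one 10cc kit of STIMULAN Rapid Cure per participant is to be used". The Introduction defines the study device as STIMULAN with antibiotic in bead form, so use in another form counts as not receiving it.

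The consent paragraph in Methods sets the general rule that "participants will be required to provide informed consent prior to any study procedures". It then allows an exception: "informed consent may occur post-operatively if the study device was used per protocol as the standard of care". Its only explicit removal rule is "Patients who consent to participate in study but do not receive the study device will not be considered study participants".

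On timing, the follow-up paragraph says "Baseline information will be collected during the initial hospital stay", and Appendix B puts consent in the Baseline column with the first KOOS and X-ray. Data Collection, Management, and Retention gives Subject IDs to study participants. Analysis of Results is descriptive and names no separate analysis populations.

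**The concern.** Eligibility here depends partly on what happens in the operating room. A patient can consent beforehand, receive the device with a second kit or with screws only, and then fail an entry criterion. The removal rule does not reach that patient, because the device was received. Sites could handle the same case differently: one might keep the patient, another might drop the patient along with any later infection or wound problem.

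Two further features add to the worry. Subject IDs go only to participants, so an unbroken run of IDs cannot show who was left out, and no log of device uses is described. Consent may also follow surgery with no stated deadline, so in principle enrolment could depend on the early wound course.

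With no comparison group, every reported proportion is only as good as its denominator. Infection, wound problems and complications, which Study Aims lists as secondary outcomes, would be the most exposed.

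**Working it through.** The plan has no figure to reproduce. The sample size of 30 rests on expected recruitment, with no power, precision or dropout calculation. The check is therefore a reading of the text, followed by an illustration of size.

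**Reading**

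1. *Pre-operative consent, device outside the limits.* The entry criterion is not met, so the literal reading is exclusion. No sentence points to inclusion.
2. *Post-operative consent, device outside the limits.* Excluded, because the exception applies only to conforming use.
3. *Consent, no device.* Excluded by the removal rule.
4. *The consecutive series.* It is limited to patients meeting the inclusion criteria, which include consent and conforming use. The plan does not claim to enrol every implanted patient.
5. *Consent timing.* Consent before study procedures, baseline data in the hospital stay and consent at Baseline together imply consent in hospital.

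Only case 1 lacks an explicit rule, and the text leans one way.

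**Size**

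Inputs: n = 30 (Methods); x = observed events; k = implanted patients outside the 30 (assumed).

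If none to all of the k had the event, the proportion among all implanted lies between x/(30+k) and (x+k)/(30+k). The width is k/(30+k), whatever x is:

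| k | width |
|---|---|
| 1 | 1/31 = 3.2 points |
| 2 | 2/32 = 6.25 points |
| 3 | 3/33 = 9.1 points |
| 5 | 5/35 = 14.3 points |

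For scale, one event in 30 is 1/30 = 3.3 points.

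The next table compares the worst case with the exact (Clopper-Pearson) 95% interval from the 30 alone. The row x = 3 is 10%, the low end of the 10 to 14% infection rate in the Introduction.

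| x/30 | exact 95% CI | last k with worst case inside | first k with worst case outside |
|---|---|---|---|
| 0/30 | 0 to 11.6% | k=3: 3/33 = 9.1% | k=4: 4/34 = 11.8% |
| 1/30 | 0.1 to 17.2% | k=5: 6/35 = 17.1% | k=6: 7/36 = 19.4% |
| 3/30 | 2.1 to 26.5% | k=6: 9/36 = 25.0% | k=7: 10/37 = 27.0% |

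Even if every uncounted patient had the event, three to six of them are needed to use up the uncertainty that 30 patients already carry.

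**The case for a change.** The strongest reply is that sampling error and an unknown denominator differ in kind. A confidence interval shows the first to the reader; an unreported k cannot be bounded at all. A device log is cheap, and reasons for non-enrolment are hard to recover afterwards. Someone exposed to the device outside its limits is also someone whose complications a reader would want to see.

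Part of this stands. The text is silent on the consented patient with non-conforming use, and a participant flow count would be good reporting practice. It does not show that a stated rule gives a wrong result, and the obvious remedies gain little:

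- Keeping such patients in the safety summaries while leaving the entry criterion as it is would contradict the criterion. It would also raise new questions: whether they count toward the 30, and whether they have the six-month CT.
- Requiring consent before discharge leaves open the very window in which early wound problems could influence enrolment, and it loses late consents.
- A log would mix non-conforming recipients, decliners and patients never approached. It would give k but no outcomes for those who did not consent, and so only wide bounds on a proportion the plan does not undertake to estimate. Recording non-consenting patients may also need ethics review at each site.

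The case report forms are not in the documents and may already capture some of this.

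**Conclusion.** The concern does not call for a change to the plan. It identifies a missing detail: one category of patient with no explicit rule, for whom the inclusion criterion and the post-operative consent condition both point to exclusion. Restricting resorption and subsidence to conforming use is an open design choice. An analyst can follow the literal reading, list any consented patient with non-conforming use as a protocol deviation, and give whatever flow counts the sites hold.

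The effect cannot be derived from the documents, in size or direction. Under the extreme assumption that every uncounted patient had the event, the worst case stays inside the exact 95% interval for up to 3 such patients with 0/30 events, 5 with 1/30 and 6 with 3/30. Larger values of k would matter more, but nothing in the documents suggests them. No test or power calculation is involved. The exposed outcomes are mainly secondary and descriptive, and selection on early wound course is possible but not shown.

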APPENDIX B

Schedule of Events

| | Baseline | 6 weeks | 3 months | 6 months | 12 months |
|------------------------------------|----------|---------|----------|----------|--------------|
| Informed Consent | X | | | | |
| Clinic Visit and CRF Completion | X | X | X | X | X |
| Range of Motion | | X | X | X | X |
| KOOS questionnaire | X | X | X | X | X |
| Assess for Adverse Events | Х | X | X | X | X |
| X-ray (AP & lat) | X | X | X | X | X |
| CT scan | | | | X | |

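### Does post-operative consent without a stated deadline let sites choose patients after early results are known?

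*Combined protocol and SAP*

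**What the plan says.** The Methods section sets the sampling rule: "Thirty (30) consecutive patients who meet the inclusion criteria will be recruited for the study and followed for one year". Two of the inclusion criteria are "Internal fixation and use of study device per protocol" and "Signed informed consent to participate in study".

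The consent paragraph after the exclusion criteria gives a general rule, that "participants will be required to provide informed consent prior to any study procedures". It then gives an exception, on the ground that the device is already a treatment option for this injury: "informed consent may occur post-operatively if the study device was used per protocol as the standard of care". It closes with "Patients who consent to participate in study but do not receive the study device will not be considered study participants".

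Three other places bear on timing:

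- The follow-up paragraph under Preparation of the Study Device says "Baseline information will be collected during the initial hospital stay".
- The outcome-measures section ties collection of demographics, history and medications to the moment of study inclusion.
- Appendix B has "Informed Consent | X" in the Baseline column and no consent entry at any later visit. It also schedules a KOOS and an adverse-event assessment at Baseline.

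No section describes a log of eligible, device-treated patients who were not enrolled. The case report forms are not among the documents, so one can say only that such a log is not described.

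**The concern.** In a single-group descriptive study the case series is the result. If a patient can be approached after surgery, the operative outcome and any early complication may already be known to the person asking and to the person deciding. Patients who are doing badly may be asked less often or may decline more often. Infection, wound problems and other complications are named secondary outcomes, and selection of that kind would lower their observed rates with no control group to reveal it.

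The wording invites this reading. The exception gives no latest day, enrolment depends on the device having been used as the protocol requires, and consented patients who do not receive the device drop out of the count. Without a record of treated patients who were not enrolled, a reader of the final report could not confirm that the series was consecutive.

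**Working it through.** **Is consent timing open-ended?** Four statements have to hold together: consent precedes any study procedure (Methods); demographics and history are taken at study inclusion (outcome-measures section); baseline information is collected in the initial stay (follow-up paragraph); consent is a Baseline item only (Appendix B). They fit together only if inclusion falls within the index admission. The Baseline KOOS supports this, because a self-completed questionnaire cannot be filled in from the chart. Enrolling someone at a later clinic visit would depart from the schedule.

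**Do the two consent sentences conflict?** No. The device and the operation are described as standard care, so surgery is not a study procedure. Consent given after surgery can still precede every study procedure.

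**Does the device condition select on outcome?** Not by itself. Whether the device was used is settled in the operating room. The condition defines the population, and consecutive refers to patients who meet criteria that include device use and consent.

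**How large could the bias be?** The plan gives no figure to reproduce: N = 30 rests on expected recruitment, with no error rate, power or effect size. The effect can only be illustrated.

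Inputs:

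- p = true infection rate, 10% to 14% (Introduction / Background, the only complication rate given).
- n = 30 (Methods).
- e = share of infections apparent before the approach. Not in the documents; assumed.
- r = enrolment of those patients relative to others. Not in the documents; assumed.

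Formula: with g = e(1 − r), observed rate = p(1 − g)/(1 − pg). It treats every patient as consented after surgery, which overstates the effect, since the plan only permits this. Missing infections are 30p minus 30 times the observed rate, with 30p = 3.0 at 10% and 4.2 at 14%.

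| e | r | g | Observed if p = 10% | Observed if p = 14% | Infections missing in 30 |
|---|---|---|---|---|---|
| 0.5 | 0 | 0.50 | 0.050/0.950 = 5.3% | 0.070/0.930 = 7.5% | 1.4 to 1.9 |
| 0.5 | 0.5 | 0.25 | 0.075/0.975 = 7.7% | 0.105/0.965 = 10.9% | 0.7 to 0.9 |
| 0.1 | 0 | 0.10 | 0.090/0.990 = 9.1% | 0.126/0.986 = 12.8% | 0.3 to 0.4 |
| 0.1 | 0.5 | 0.05 | 0.095/0.995 = 9.5% | 0.133/0.993 = 13.4% | 0.1 to 0.2 |

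The rows with e = 0.5 suppose that half of a year's infections are visible before the patient is asked. That is hard to square with enrolment during the initial stay. The rows with e = 0.1 are closer to the plan as written, although the documents support no particular value.

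**Against sampling error.** The Clopper–Pearson 95% interval is 2.1% to 26.5% for 3/30 and 0.8% to 22.1% for 2/30. Even one whole missing infection is small beside that width.

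**Are the main outcomes exposed?** Hardly. The plan expects resorption by three months and remodelling by six, and subsidence is read from CT at six months. None of these is known during the initial stay.

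**The case for a change.** The strongest reply is that the admission limit is inferred. No sentence makes it a deadline, and the narrative places KOOS only at follow-up visits, so the Baseline KOOS rests on Appendix B alone. Visits and radiographs are routine, and most other baseline items could be taken from the chart. Even with consent confined to the admission, the operative result and in-hospital wound or fixation problems can be known before the patient is asked. Peri-operative events are among the adverse events of interest, and 2/30 reads differently from 3/30 in a report meant to guide surgeons. A deadline and a log would cost little.

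Part of this stands. The deadline is implied, and without a log nobody could later show that enrolment was consecutive. Some under-counting of in-hospital events remains possible. But requiring consent before discharge would restate what the schedule implies and would leave selection on in-hospital events exactly where it is. A log would make selection visible in the report without altering any estimate. A site that takes consecutive eligible patients and consents them at Baseline is already barred from picking by outcome; refusals remain, as in any study that needs consent.

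**Conclusion.** The concern does not call for a change. Post-operative consent is a fair trade-off where the treatment is standard care and eligibility depends on what was implanted. The remaining sections of the plan supply the time limit that the consent sentence omits. Followed as written, the series is sound for its descriptive purpose.

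At the illustrative e = 0.1, the shortfall is about 0.1 to 0.4 infections in 30, on secondary outcomes only and well inside sampling error. The larger figures, up to 1.9 infections, need half of all infections to be known before the approach, which is in tension with enrolment in the index admission. Both values of e are assumptions, and the true size of any bias cannot be derived from the documents.

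What is left is a matter of reporting: whoever writes up the study would sensibly count events from the day of surgery, give the flow of device-treated patients where sites can supply it, and call the series consecutive only if that flow supports the word. The conclusion rests on reading the Baseline entries as falling within the initial stay. Evidence that sites were enrolling at later clinic visits would reopen it.

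### The adverse events of interest do not name events related to the study device or its antibiotic, and the analysis section does not summarise such events

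*Combined protocol and SAP*

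**What the plan says.** The Adverse Events paragraph (under How Will The Outcome Measures Be Measured at Follow-up?) makes three statements.

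- On routine safety follow-up, "monitoring of adverse events will be according to standard clinical practice", on the ground that the device is used within its indications.
- Serious events have a separate route: the protocol says "Reporting of serious adverse events will be according to the REB policy at participating sites, with copies sent to the lead site". The manufacturer's quality department is copied too. This route is not limited by type of event.
- The scope is then set: "Adverse events of interest in the study are those associated with the surgical procedure and healing of the injury".

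Other sections bear on the point:

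- **Introduction / Background** defines the study device as the calcium sulfate product combined with antibiotic, in bead form.
- **Preparation of the Study Device**: "The selection of antibiotic from those in the mixing guidelines is left to the surgeon's discretion". The agent can therefore differ between participants.
- **Exclusion Criteria** include "Hypercalcaemia" and "Renal-compromised patients", with no reason given for either.
- **Study Aims** list infection, wound problems and complications among the secondary outcomes. Complications are not defined.
- **Analysis of Results** is descriptive. Its safety items are local: graft loss or early resorption, failed fixation, and infection. It has no general adverse-event summary. Its explanatory factors are tobacco use, age, sex and fracture class, and do not include the antibiotic.
- **Appendix B** schedules an adverse-event assessment at baseline, 6 weeks, 3, 6 and 12 months, without saying which events count.

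**The concern.** What this trial adds to earlier work is the antibiotic in the graft. Why is a Trial Needed Now? notes that the earlier resorption studies used calcium sulfate without one. The only sentence telling sites which adverse events matter nevertheless refers to the operation and the fracture, and not to the implanted material.

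A site that follows the sentence closely could treat a mild renal, calcium or allergic event some weeks after surgery as outside the events of interest. Another site could count it as a consequence of the operation. Up to four centres are planned, so such events could be classified differently between them.

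At stake is how a safety statement can be read. The results are meant to guide surgeons. If the report shows few or no device-related events, a reader could not tell how far that reflects their absence and how far it reflects what sites were asked to note.

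**Working it through.** The documents state no figure on this point, so there is nothing to reproduce. The main check is a comparison of the text.

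**Step 1: which events have a route into the results?**

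| Type of event | Named as of interest | Other route | Summarised in Analysis of Results |
|---|---|---|---|
| Local surgical or healing event | Yes | Visit assessment | Yes for graft, fixation and infection |
| Serious systemic event | Not named | Serious-event reporting; visit assessment | No |
| Non-serious device- or antibiotic-related systemic event | Not named | Visit assessment only, with no instruction to include it | No |

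The gap is the third row, together with the missing summary in the last column. No other section brings these events in. Complications in Study Aims might include them, but the term is undefined.

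**Step 2: what could 30 participants show?** The sample size of 30 comes from Methods and was chosen on expected recruitment. The true rates p are assumptions, since the documents give none. The chance of at least one event is 1 − (1 − p)^30:

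- p = 1%: 1 − 0.99^30 = 0.260
- p = 2%: 1 − 0.98^30 = 0.455
- p = 5%: 1 − 0.95^30 = 0.785
- p = 10%: 1 − 0.90^30 = 0.958

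These results presume that every event comes to light and is recorded. If only half did so (a further assumption), the effective rate would be p/2. A true 10% would then behave like 5% (0.785 in place of 0.958), and a true 2% like 1% (0.260 in place of 0.455).

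**Step 3: what would zero events mean?** With complete recording in 30 participants, the exact one-sided 95% upper limit is 1 − 0.05^(1/30) = 9.5%. The upper end of the two-sided 95% interval is 1 − 0.025^(1/30) = 11.6%. Even full recording could not exclude uncommon harm. With incomplete recording, not even these limits can be claimed.

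**The case against.** The case on the other side has real weight.

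- **Collection is not barred.** Calling some events of interest sets a focus. Adverse events are assessed at baseline and at all four follow-up visits without limit by type, and serious events have their own route. A reader might infer that non-serious systemic events would go uncollected. The documents do not say that. They only fail to require that such events be recorded as of interest or summarised.
- **The sentence can be read broadly.** The beads are placed during the operation, so their effects could count as associated with it, and no time limit is set. That reading is reasonable, but the text does not state it, and the ambiguity is itself a reason to clarify.
- **The exclusions prove little.** A reader might infer from the hypercalcaemia and renal exclusions that the plan itself regards calcium load and antibiotic clearance as risks. The exclusions are consistent with that, but the protocol gives no reason for them and the list mixes many kinds of condition.
- **Missing evidence concerns effectiveness.** A reader might take the protocol to say that safety evidence is lacking. It says there is no published evidence of effectiveness in this indication, and it describes calcium sulfate as having a proven safety record.
- **Light monitoring is a stated choice**, justified by use within indications and by risk no greater than standard care. This explains why no tests are added. It does not explain why device-related events already found in usual care should be left unnamed.
- **The forms cannot be checked.** The case report forms are not included and the content of Appendix A is not shown, so the relevant fields may already exist. The fix is conditional for that reason.

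**Conclusion.** The point holds as a gap in scope and reporting. The protocol does not name device- or antibiotic-related events among those of interest, and the analysis does not summarise them. Non-serious events of this kind may therefore be recorded unevenly or missed in the results, and a low count could partly reflect scope.

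The documents do not support the stronger conclusion that the trial will produce a false safety claim. No statement that device-related events were absent is planned, safety is not the primary aim, and serious events are reported whatever their type.

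Nor can the 45%, 79% and 96% figures be read as detection chances that the present wording throws away. They rest on assumed rates and on events coming to light in usual care. Some events would be captured under the present wording, and silent ones would stay undetected under the fix as well.

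Severity is minor to moderate.

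**What to change.** 1. In the Adverse Events paragraph, extend the scope sentence so that it also covers events associated with the study device or its antibiotic, including systemic effects.
2. On the case report form, if not already there, record the antibiotic and the amount implanted, and add fields for calcium, renal and hypersensitivity events found in usual care.
3. In Analysis of Results, add a descriptive listing of all adverse events that shows the antibiotic used for each participant concerned. A listing suits 30 participants better than rates or comparisons by antibiotic.

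The change adds no test, visit or clinical rule. Whether laboratory monitoring is warranted is a clinical decision for the investigators and is not part of this point.

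The cost is one sentence, a few fields at visits where adverse events are already assessed, and one listing. The downsides are slightly more data entry, possibly a less favourable safety table, and small counts for each antibiotic.
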